6.5 Permitted dose adjustments and discontinuation of study treatment

Every attempt should be made to maintain patients at the target study drug dose level throughout the trial. If the patient does not tolerate the target study drug dose level the investigator can, if appropriate, adjust concomitant background medications for co-morbid conditions to rectify the situation, and if necessary down titrate to the next lower study drug dose level. Any dose-adjustment of disease-modifying background therapy, e.g. beta-blockers or MRAs is discouraged.

Down-titration of the study drug at any time will be allowed based on the safety and tolerability criteria defined in Table 4-3 and section 6.8. If down-titration is necessary, the patient should be down-titrated to the next lower dose level (Table 4-2) The patient may continue receiving the lower dose level for a recommended period of 1 to 4 weeks before re-challenging the patient with the next higher dose level. For example, a patient who encounters tolerability problems at the target dose level (dose level 3), should receive the study drug at dose level 2 for 1 to 4 weeks. Then, he/she should be re-challenged with up-titration back to dose level 3. If the tolerability issues are not alleviated despite down-titration by one dose level, the investigator may lower the study drug dose further to the next lower level for 1 to 4 weeks, up to temporary withdrawal of the study drug. Study drug should be reintroduced in those who temporarily discontinue it as soon as medically justified in

the opinion of the investigator. Again, once stable, the patient should be re-challenged with up-titration to the next higher dose level every 1 to 4 weeks in an attempt to bring back the patient gradually to the target study drug dose level (dose level 3). The investigator may choose the next dose level for down- or up-titration according to his or her judgement.

In some instances, according to the safety and tolerability criteria and the investigator's judgment, dose level 1 or 2 could be maintained if he/she considers that the patient's condition would not allow any further up-titration to the target dose of study medication (level 3). In this case it would be acceptable to maintain the patient at dose level 1 or level 2, whichever is the higher and tolerated dose level by the patient.

Any dose change must be recorded on the dosage administration record on the eCRF.

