Should a patient develop symptomatic heart failure during the study they will be offered open-label sacubitril/valsartan. Patients starting open-label sacubitril/valsartan or withdrawing from study medication (or study follow-up) ≥ 6 months after randomisation will be asked to undergo an end-of-study CMR examination (patient withdrawing before 6 months will not be asked to have a second CMR as an effect of LV remodelling is unlikely to be detected before this time point).

The emergence of the following circumstances will require permanent study drug discontinuation:

- Withdrawal of informed consent
- Investigator thinks that continuation of study drug would be detrimental to the patient's well-being
- Suspected or confirmed occurrence of clinically significant angioedema. A patient with any signs or symptoms of clinically significant angioedema should be thoroughly evaluated by the investigator
- Pregnancy and post-pregnancy during lactation period

The emergence of the following circumstances will require temporary or permanent discontinuation (study drug may be restarted once these circumstances no longer exist):

- Use of an open label ACE inhibitor, ARB, direct renin inhibitor, lithium, cholestyramine or colestipol resins (*Table 6-1*)
- Any laboratory abnormalities that in the judgment of the investigator warrant discontinuation of study drug after taking into consideration the patient's overall condition

Study drug may be discontinued at the investigator's discretion if any of the following occurs:

- Any severe suspected drug-related AE

- Any other protocol deviation that results in a significant risk to the patient's safety
- Subsequent clinical need for implantable cardiac device insertion (e.g. permanent pacemaker, implantable cardioverter defibrillator, cardiac resynchronisation therapy)

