Any ARB	Discontinue study drug. The open label ARB must be stopped prior to re-initiation of study drug
Any direct renin inhibitor	Discontinue study drug. The open label direct renin inhibitor must be stopped prior to re-initiation of study drug
Entresto (commercially available sacubitril/valsartan)	Discontinue study drug. The open label Entresto must be stopped for ≥ 36 hours prior to re-initiation of study drug
Lithium	Discontinue study drug. Lithium must be stopped prior to re-initiation of study drug
Cholestyramine or colestipol resins	Discontinue study drug. Cholestyramine or colestipol resins must be stopped prior to re-initiation of study drug

The concomitant use of open-label ACE inhibitor, ARBs, commercially available sacubitril/valsartan (Entresto) or a direct renin inhibitor is **strictly prohibited** while the patient is receiving study drug. If the addition of an ACE inhibitor, ARB, Entresto or direct renin inhibitor is necessary, then study drug must be temporarily discontinued. If the patient is to be started on open-label ACE inhibitor or Entresto, the study drug must be stopped ≥ 36 hours prior to initiating ACE inhibitor or Entresto. If study drug is to be re-started, the open-label ACE inhibitor or Entresto must also be stopped ≥ 36 hours prior to re-initiating study drug. ARBs or a direct renin inhibitor should be stopped prior to resuming study drug.

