6.8.4 Management of angioedema

Angioedema is a potential side effect of combined RAAS and NEP inhibition. Angioedema has been reported in patients treated with sacubitril/valsartan. If angioedema occurs, study drug should be immediately discontinued and appropriate therapy and monitoring should be provided until complete and sustained resolution of signs and symptoms has occurred. It must not be re-administered. Any patients who experience angioedema during the trial will be withdrawn from the study.

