10.2 Recording and reporting of Adverse Events

All AEs occurring during the trial that are observed by the Investigator or reported by the participant should be recorded in the participant's medical records whether or not attributed to trial medication.

Details of the following adverse reactions will be collected within the eCRF at all follow up visits from randomisation until the participants' final visit.

- Clinically relevant hypotension (syncope, dizziness, etc)
- Worsening renal function
- Acute kidney injury
- Hyperkalaemia
- Occurrence of angioedema

The seriousness of each adverse reaction will be collected along with the outcome of the event at the time of the visit i.e. whether the reaction is ongoing at the time of the visit or the participant has recovered.

SAEs will be documented within the eCRF and will be collected from the date of randomisation until 30 days post cessation of trial treatment to allow for reporting of any ongoing adverse reactions associated with the use of the trial drug.

The following events are excluded from the need for expedited reporting:

- Routine treatment or monitoring of the studied indication not associated with any deterioration in condition.
- Treatment which was elective or pre-planned, for a pre-existing condition not associated with any deterioration in condition, e.g. pre-planned hip replacement operation which does not lead to further complications.
- Any admission to hospital or other institution for general care where there was no deterioration in condition.
- Treatment on an emergency, outpatient basis for an event not fulfilling any of the definitions of serious as given above and not resulting in hospital admission.

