2.1. STUDY POPULATION

The analysis population will comprise of all subjects randomised into the study.

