2.5.2. ADVERSE EVENTS OF INTEREST

Adverse events of interest include:

- Worsening renal function or acute kidney injury
- Hyperkalaemia
- Symptomatic hypotension
- Symptomatic hypotension with systolic BP <90mmHg
- Angioedema
- Cough

The number and percentage of subjects experiencing one of the adverse events of interest listed will be summarised overall and by randomised treatment group. The Fisher's Exact test will be used to assess whether there is a statistical difference between number of subjects experiencing each event between treatment groups. The following event details will also be summarised and compared between groups: seriousness criteria, severity, relationship to study drug and details of action taken. Full details of these events are provided in section 10.2 of the study protocol.

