2.5.3. SERIOUS ADVERSE EVENTS

The number of serious adverse events will be reported and the following event details will be summarised for the randomised population overall and by treatment group: seriousness criteria, severity, relationship to the study drug, expectedness, event outcome and SAE duration (if recovered or fatal).

The number and percentage of subjects experiencing at least one serious adverse event will be reported and summarised by Medical Dictionary for Regulatory Activities (MedDRA) System Organ Class (SOC) and Preferred Term (PT). The Fisher's Exact test will be used to assess whether there is a statistical difference between the number of subjects with each type of event between treatment groups.

The same summaries will be provided for the subsets of serious adverse events that are (a) at least possibly related to the study treatment, (b) Suspected Unexpected Serious Adverse Reactions (SUSARs) and (c) fatal, (d) prior to 1st March 2020 and (e) experienced on or after 1st March 2020.

All serious adverse events will be listed.

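### Adverse events of interest are tabulated only by randomised arm, so an event on open-label sacubitril/valsartan in a valsartan-arm patient still in follow-up would count under valsartan

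*SAP*

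**What the plan says.** - SAP 2.1 defines one population: "The analysis population will comprise of all subjects randomised into the study". Neither document defines a safety, as-treated or on-treatment set.
- SAP 2.5.2, on hypotension, renal events, hyperkalaemia, angioedema and cough: "The number and percentage of subjects experiencing one of the adverse events of interest listed will be summarised overall and by randomised treatment group". Each event is then compared between arms with Fisher's exact test. Relationship to study drug is also summarised.
- SAP 2.5.3 treats serious adverse events (SAEs) in the same way: details are "summarised for the randomised population overall and by treatment group". There is a subset for events at least possibly related to treatment, and a listing of every SAE.
- Protocol 6.5: "Should a patient develop symptomatic heart failure during the study they will be offered open-label sacubitril/valsartan". The offer is not restricted to one arm. Protocol 6.6 adds: "If the patient is to be started on open-label ACE inhibitor or Entresto, the study drug must be stopped ≥ 36 hours prior".
- Protocol 10.2 gives two collection windows. Details of hypotension, worsening renal function, acute kidney injury, hyperkalaemia and angioedema "will be collected within the eCRF at all follow up visits from randomisation" up to the final visit, with no cut-off when study drug stops. SAEs are collected until 30 days after trial treatment stops.
- On data available, protocol 6.5 says: "Any dose change must be recorded on the dosage administration record on the eCRF". Protocol 6.6 and the schedule of assessments have concomitant medication reviewed at every visit.

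**The concern.** Comparison by randomised arm keeps the benefit of randomisation and should stay. As the only safety presentation, it does not show which drug a patient was taking when an event occurred. That matters here because the rescue drug is the experimental drug. A sacubitril/valsartan patient who goes open-label stays on the same active drug. A valsartan patient who goes open-label takes on the other arm's exposure, and later events are still counted under valsartan. This route can therefore only narrow an excess of harm on sacubitril/valsartan.

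The events concerned are those that section 2.5.2 exists to compare. For one of them the protocol notes: "Angioedema has been reported in patients treated with sacubitril/valsartan". The causality summaries do not solve this. Relatedness is a judgement about cause, not a record of exposure, and the SAP does not say whether open-label sacubitril/valsartan counts as study drug. Only SAEs are promised a full listing, so a reader could not trace the exposure behind a non-serious event of interest.

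**Working it through.** **Inputs from the documents.** The plan has 45 evaluable patients per arm and 10% discontinuation (protocol 11.1): 90 / (1 − 0.10) = 100 randomised, or 50 per arm. The 10% covers loss to follow-up, heart failure and death together. As a planning rate it gives 0.10 × 50 = 5 patients per arm for all three causes. The plan gives no figure for switching or for event rates, so there is none to reproduce.

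**Assumptions.** 1 to 5 valsartan-arm switchers; 12-month risks of 20% on sacubitril/valsartan (pS) and 10% on valsartan (pV), with 30% and 15% as a second case; constant hazards over a 12-month follow-up; a fraction f of follow-up spent on open-label drug and still counted.

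**SAE window.** Collection ends 30 days after trial treatment stops, and at least 36 hours (1.5 days) must pass before open-label drug starts. This leaves at most 30 − 1.5 = 28.5 days of open-label exposure, if trial treatment means the randomised drug and it is not restarted.

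**Formula.** A switcher's 12-month risk is 1 − (1 − pV)^(1−f) × (1 − pS)^f. The valsartan-arm risk rises by s × (that risk − pV) / 50 for s switchers.

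**Switch at mid-trial, counted to the end (f = 0.5), 20% v 10%.** The switcher's risk is 1 − √(0.90 × 0.80) = 0.1515, an increase of 0.0515.
- s = 1: 0.0515 / 50 = 0.10 points.
- s = 5: 5 × 0.0515 / 50 = 0.51 points, or 0.26 extra patients. The difference reads 9.5 points instead of 10.0.

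**Whole-year exposure (f = 1), s = 5.** 5 × (0.20 − 0.10) / 50 = 1.0 point. This is an outer limit: heart failure is excluded at entry, so nobody should switch on day 0.

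**Counting stops at 30 days (f = 30/365), s = 5.** The switcher's risk is 0.1087, so 5 × 0.0087 / 50 = 0.09 points, or 0.04 extra patients.

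**Higher risks (30% v 15%), f = 0.5, s = 5.** The switcher's risk is 1 − √(0.85 × 0.70) = 0.2286, so 5 × 0.0786 / 50 = 0.79 points. The difference reads 14.2 instead of 15.0.

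**Patients expected to have an event while on open-label drug**, s × [1 − (1 − pS)^f]: at mid-trial, from 1 × (1 − √0.80) = 0.11 to 5 × (1 − √0.70) = 0.82. With 30 days counted, from 0.02 to 0.14.

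**Effect of one whole patient in a sparse table** (two-sided Fisher, 50 per arm, counts chosen for illustration):

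| Counts (sacubitril/valsartan v valsartan) | p | One more valsartan-arm patient | p |
|---|---|---|---|
| 6 v 0 | 0.027 | 6 v 1 | 0.112 |
| 8 v 1 | 0.031 | 8 v 2 | 0.092 |
| 1 v 0 | 1.00 | 1 v 1 | 1.00 |

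In the last row the p-value does not move, but the table no longer shows angioedema on one drug only.

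**The case against.** Five objections carry weight.

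1. **Switchers may leave follow-up.** Collection stops at the participant's final visit. Protocol 6.5 asks those who switch at 6 months or later for an end-of-study scan, and protocol 11.1 counts heart failure as discontinuation. If a switch ends follow-up, little is left to misattribute. The documents do not settle this, so the concern is conditional. The silence is itself a gap to close.
2. **SAEs are largely protected.** A reader might infer that all safety events are affected. The 30-day limit does not support that: SAE data are already close to on-treatment.
3. **The average effect is small.** A reader might add the open-label risk to a full year of valsartan risk: 5 × 0.90 × 0.20 / 50 = 1.8 points, or 18% of the excess. That counts the same months twice. Dividing the year between the drugs gives 0.5 points at mid-trial and 1.0 at most. Trial size limits the comparison far more: for 20% v 10% with 50 per arm, Fisher power is about 19%, and about 17% after the mid-trial dilution from five switchers.
4. **Other drugs enter too.** Under protocol 6.9, patients who withdraw in either arm move to an ACE inhibitor or ARB. The one-way argument therefore holds for open-label sacubitril/valsartan only, and a cut-off at that drug alone would be incomplete.
5. **Randomised-arm analysis follows the protocol.** Section 11.3 specifies intention to treat, and the relatedness summaries and SAE listing allow some separation. This justifies keeping the present tables. It does not supply a summary by exposure.

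**Conclusion.** The gap is real and modest. SAP 2.5.2 has no summary that separates events on randomised drug from events on open-label sacubitril/valsartan, and the collection rule for the listed reactions does not stop at a switch. If switchers stay in follow-up, each one at mid-trial moves the valsartan rate by about 0.1 points under assumed risks of 20% and 10%. Five move it by about 0.5 points, or 0.8 under 30% and 15%. These sizes rest on assumed risks, constant hazards and 1 to 5 switchers. The 10% behind the upper figure is a planning rate, not a cap.

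A reader might infer that the tables could reverse a true excess. On average they could not, since no scenario at 20% v 10% removes more than a tenth of it. The risk lies in sparse events, where a single case placed under the wrong drug changes how the table reads. The change is worth making because it needs no new data.

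**What to change.** Keep the randomised-arm tables as they are, and amend the SAP as follows:

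- **2.1:** add a safety set of randomised patients who took at least one dose of study drug.
- **2.5.2, and 2.5.3 for consistency:** add a supplementary on-treatment summary in that set. Count events from first dose to the earlier of 30 days after the last study dose, or the start of any open-label sacubitril/valsartan, ACE inhibitor or ARB.
- **Same sections:** show events after the start of open-label sacubitril/valsartan separately, labelled by that drug and by randomised arm.
- **2.5.2:** state how long adverse events of interest are collected after a switch, and how events are classified if study drug is later restarted, which protocol 6.6 allows.

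The cost is SAP wording and one extra set of tables, built from the dosing record and concomitant medication data already collected. The on-treatment version will have slightly fewer events, and it is cut at a time that depends on the patient's condition. It therefore supplements the randomised-arm table and does not replace it. No dosing, rescue or stopping rule changes.

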2.5.3. SERIOUS ADVERSE EVENTS

The number of serious adverse events will be reported and the following event details will be summarised for the randomised population overall and by treatment group: seriousness criteria, severity, relationship to the study drug, expectedness, event outcome and SAE duration (if recovered or fatal).

The number and percentage of subjects experiencing at least one serious adverse event will be reported and summarised by Medical Dictionary for Regulatory Activities (MedDRA) System Organ Class (SOC) and Preferred Term (PT). The Fisher's Exact test will be used to assess whether there is a statistical difference between the number of subjects with each type of event between treatment groups.

The same summaries will be provided for the subsets of serious adverse events that are (a) at least possibly related to the study treatment, (b) Suspected Unexpected Serious Adverse Reactions (SUSARs) and (c) fatal, (d) prior to 1st March 2020 and (e) experienced on or after 1st March 2020.

All serious adverse events will be listed.

3. DOCUMENT HISTORY

This is version 1.1 of the SAP for the RECOVER-LV study, the second version of this document.

4. TABLES, FIGURES AND LISTINGS

Summary tables and figures will be generated prior to database lock. Approval of the content of these documents will then be required for database lock.
